## 7.3.3. Subgroup Analyses for Primary Endpoints

Subgroup analysis will be performed based on the following participant demographics and baseline disease characteristics variables for those participants whose data are available:

- Baseline IGA-CHE score (3, 4)
- Age ( $\ge 18$  to 64,  $\ge 65$  years)
- Sex (male, female)
- Race
- Region (North America or outside of North America)

## 7.4. Analysis of the Secondary Efficacy Parameters

## 7.4.1. Key Secondary Efficacy Measure

#### 7.4.1.1. Chronic Hand Eczema-Related Itch Numerical Rating Scale Score

The CHE-related Itch NRS is a once-per-24 hours ("daily") patient-reported measure of the worst itch severity of their CHE assessed using an 11-point scale (0 = no itch to 10 = worst imaginable itch). Participants reported their worst itch severity in the evening beginning on the day of screening through Week 32 or ET.

The CHE-related Itch NRS score for baseline will be determined by averaging the 7 daily NRS scores before Day 1 (Day –7 to Day –1). The by-visit CHE-related Itch NRS score for postbaseline visits will be determined by averaging the 7 daily NRS scores before the visit day. If 4 or more daily scores are missing (out of the 7), the CHE-related Itch NRS score at the visit will be set to missing. For all daily itch related analyses including time to achieve Itch NRS score improvement of at least 2 or 4 points, baseline will be defined as the last available Itch NRS score during the last week prior to Day 1 (from Day –7 to Day –1).

The proportion of participants with a clinically relevant change in CHE-related itch (ITCH4), defined as  $a \ge 4$ -point improvement in CHE-related Itch NRS score from baseline, will be summarized by treatment groups.

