5.1. Inclusion Criteria

Participants are eligible to be included in the study only if all of the following criteria apply:

- 1. Ability to comprehend and willingness to sign a written ICF for the study.
- 2. Age \geq 18 years at the screening visit.
- 3. Diagnosis of CHE for at least 6 months prior to screening.
 - Diagnosis of CHE is defined as HE lasting > 3 months or ≥ 2 recurrences within the previous 12 months.
 - *Note:* Participants with hyperkeratotic, vesicular (eg, pompholyx), and fingertip eczema may be included.
- 4. Screening and baseline IGA-CHE score of 3 or 4.
- 5. Baseline CHE-related Itch NRS score ≥ 4. Baseline Itch NRS score is defined as the 7-day average of Itch NRS score directly before Day 1 (data from a minimum of 4 out of 7 days prior to Day 1 is needed).
- 6. Have been treated with at least 1 prescription CHE therapy or if such therapy was not advisable or contraindicated.
- 7. Willingness to avoid pregnancy or fathering children based on the criteria below.
 - a. Male participants with reproductive potential must agree to take appropriate precautions to avoid fathering children from screening through 90 days (a spermatogenesis cycle) after the last application of ruxolitinib cream and must refrain from donating sperm during this period. Permitted methods in preventing pregnancy (see Appendix A) should be communicated to the participants and their understanding confirmed.
 - b. Female participants who are WOCBP must have a negative serum pregnancy test at screening and negative urine pregnancy test before the first application on Day 1 and must agree to take appropriate precautions to avoid pregnancy from screening through 30 days (1 menstrual cycle) after the last application of study ruxolitinib cream and must refrain from donating oocytes during this period. Permitted methods in preventing pregnancy (see Appendix A) should be communicated to the participants and their understanding confirmed.
 - c. Female participants not considered to be of childbearing potential as defined in Appendix A are eligible.

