8.2.6. Patient-Reported Outcomes

Patient-reported outcomes will be assessed as outlined in the SoA (see Table 3).

8.2.6.1. eDiary Assessments

Participants will be issued a handheld device (eDiary) for daily assessments at the screening visit. The participant will be instructed to complete and record the CHE-related Itch NRS and Skin Pain NRS via an eDiary daily, in the evening beginning on the day of screening through Week 32 or ET.

Both the Itch NRS and Skin Pain NRS are a daily participant-reported measure (24-hour recall) of the worst level of itch or skin pain intensity related to CHE.

The participants will rate the following:

• CHE-related Itch NRS: Itch severity of their CHE by selecting a number from 0 (no itch) to 10 (worst imaginable itch) that best describes their worst level of itching in the past 24 hours.

• CHE-related Skin Pain NRS: Pain severity of their CHE by selecting a number from 0 (no pain) to 10 (worst imaginable pain) that best describes their worst level of pain in the past 24 hours.

The average of 7-day CHE-related Itch NRS prior to the baseline visit (minimum 4 out of 7 days' data required) will be used to determine if a participant meets the inclusion criteria.

Detailed directions for the administration of an eDiary will be provided in the Study Manual.

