10.4.2. Key Secondary Objective

If the primary objective is achieved, the statistical hypotheses for the key secondary endpoint will be tested in the order specified in Section 10.3. Key secondary efficacy analysis at Week 16, Week 4, and Week 1 (Day 7) will be conducted in the ITT population. The statistical comparisons for binary outcomes (ITCH4) will be analyzed using a similar method as specified in the primary analysis. The stratum-adjusted ITCH4 rate difference (1.5% BID vs vehicle) and 95% CI will be computed in a similar way as in the primary analysis. A summary of analyses for the key secondary endpoints is provided in Table 12.

Table 12: Summary of Analyses for Key Secondary Endpoints

Parameter	Definition
Treatment	Ruxolitinib 1.5% cream compared with vehicle cream
Population	ITT population
Variables	ITCH4 response at Week 16: Defined as a ≥ 4-point improvement in CHE-related Itch NRS score from baseline ITCH4 response at Week 4 ITCH4 response at Week 1 (Day 7)
Population-level summary	Stratum-adjusted IGA-CHE-TS rate difference with 95% CI

Note: Participants with missing observed data at the timepoint of interest, participants who discontinue study treatment at any time before the timepoint of interest, and participants who discontinue from the study for any reason will be defined as nonresponders. No rescue therapy or treatment switch is allowed in this study.

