## 7.4.2. Key Secondary Efficacy Analysis

Key secondary efficacy analyses will be conducted in the ITT population in the DBVC period. If the primary objective is achieved, the statistical comparisons for key secondary endpoints will be tested with the procedures specified in Section 3.2. The same nonresponder imputation method as specified in the primary analysis will be used to handle missing Week 4 and Week 16 itch data.

For the key secondary endpoints of ITCH4 at Week 1 (Day 7), all participants who are missing Day 7 daily Itch NRS scores will be imputed using multiple imputation by fully conditional specification method. The variables to be included in the imputation regression model are treatment group, stratification factor, baseline itch score, and postbaseline daily itch score on Day 1 to Day 7. The corresponding binary response on Day 7 will be derived for each of the imputed datasets per the definition in Section 7.4.1.1.

The following sample SAS code will be used for the MI:

```
proc mi data=mi_wide seed=18424226 nimpute=30 out=impute_itch;
class trt01p strat1 strat2;
var trt01p strat1 strat2 base avald1 avald2 avald3 avald4 avald5
avald6 avald7;
fcs regpmm nbiter=30;
run;
```

All key secondary efficacy analyses will use stratified CMH test similar to the primary efficacy analysis. The summary of key secondary endpoints analysis is also provided in Table 5.

**Table 5:** Summary of Analyses for Key Secondary Endpoints

Parameter	Definition	
Treatment	Ruxolitinib 1.5% cream compared with vehicle cream	
Population	ITT population	
Variables	ITCH4 response at Week 16 ITCH4 response at Week 4 ITCH4 response at Week 1 (Day 7)	
Population-level summary	Stratum-adjusted IGA-CHE-TS rate difference with 95% CI	

Note 1: Participants with missing observed data at the timepoint of interest (Week 4, Week 16), participants who discontinue study treatment at any time before the timepoint of interest (Week 4, Week 16), and participants who discontinue from the study for any reason will be defined as nonresponders. Participants with missing observed data at Day 7 will be imputed using multiple imputation by fully conditional specification method. No rescue therapy or treatment switch is allowed in this study. Note 2: ITCH4 is defined as  $a \ge 4$ -point improvement in CHE-related Itch NRS score from baseline.

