#### 7.5.2.2. Categorical Efficacy Endpoints

For the following categorical parameters, summary statistics including sample size, frequency, and percentages will be presented by visits.

- Proportion of participants achieving an IGA-CHE-TS
- Proportion of participants achieving ≥ 2-point improvement in CHE-related Skin Pain NRS score up to Week 16 from baseline.
- Proportion of participants achieving ≥ 4-point improvement in CHE-related daily Itch NRS score from baseline to Day 14.

Statistical analysis for the ITCH4 response at Day 3 will be conducted using models similar to the key secondary endpoint of ITCH4 at Day 7, specified inSection 7.3.2.

For the following categorical endpoints, the number and percentage of participants will be summarized by treatment at each postbaseline visit:

- Proportion of participants in each category of EQ-5D-5L score
- Proportion of participants with each score on the PGIC

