# **Figures**

Figure No.	Title	Population
4.1 IGA-CHI	E-TS	
4.1.1.1	Proportion of Participants Achieving IGA-CHE-TS in the Treatment Period	ITT
4.1.1.2	Proportion of Participants Achieving IGA-CHE-TS in the DBVC Period With Nonresponder Imputation	ITT
4.1.2.1	Proportion of Participants Achieving IGA-CHE-TS By Baseline IGA-CHE Score in the Treatment Period	ITT
4.1.2.2	Proportion of Participants Achieving IGA-CHE-TS by Age Group in the Treatment Period	ITT
4.1.2.3	Proportion of Participants Achieving IGA-CHE-TS by Sex in the Treatment Period	ITT
4.1.2.4	Proportion of Participants Achieving IGA-CHE-TS by Race in the Treatment Period	ITT
4.1.2.5	Proportion of Participants Achieving IGA-CHE-TS by Region in the Treatment Period	ITT
4.1.3	Forest Plot of Response Rate Difference in Achieving IGA-CHE-TS at Week 16	ITT

Figure No.	Title	Population
CHE-Related	l Itch NRS Score	
4.3.1.1	Proportion of Participants Achieving ≥ 4-point Improvement in CHE-Related Itch NRS Score in the Treatment Period	ITT
4.3.1.2	Proportion of Participants Achieving ≥ 4-point Improvement in CHE-Related Itch NRS Score in the DBVC Period With Nonresponder Imputation	ITT
4.3.2.1	Mean and Standard Error Plot of CHE-Related Itch NRS Score by Visit in the Treatment Period	ITT
4.3.2.2	Mean and Standard Error Plot of Change From Baseline in CHE-Related Itch NRS Score by Visit in the Treatment Period	ITT
4.3.3.1	Proportion of Participants Achieving ≥ 4-point Improvement in CHE-Related Daily Itch NRS Score from Day 1 to Day 14	ITT
4.3.3.2	Proportion of Participants Achieving ≥ 4-point Improvement in CHE-Related Daily Itch NRS Score from Day 1 to Day 7 using Multiple Imputation	ITT
4.3.4.1	Mean and Standard Error Plot of CHE-Related Daily Itch NRS Score in the Treatment Period	ITT
4.3.4.2	Mean and Standard Error Plot of Change From Baseline in CHE-Related Daily Itch NRS Score in the Treatment Period	ITT
4.3.5.1	Kaplan-Meier Curve of the Time to ≥ 4-Point Improvement in Itch NRS Score in the DBVC Period	ITT
CHE-Related	l Skin Pain NRS	
4.4.1	Proportion of Participants Achieving ≥ 2-point Improvement in CHE-Related Skin Pain NRS Score in the Treatment Period	ITT
4.4.2.1	Mean and Standard Error Plot of CHE-Related Skin Pain NRS Score by Visit in the Treatment Period	ITT
4.4.2.2	Mean and Standard Error Plot of Change From Baseline in CHE-Related Skin Pain NRS Score by Visit in the Treatment Period	ITT

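### Does measuring Day 7 ITCH4 from the last single diary score, rather than the 7-day average used at Weeks 4 and 16, undermine that test?

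*SAP*

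**What the plan says.** Protocol 5.1, criterion 5, states: "Baseline Itch NRS score is defined as the 7-day average of Itch NRS score directly before Day 1", with at least 4 of the 7 days present and a value of at least 4 needed for entry. Protocol 8.2.6.1 says this average "will be used to determine if a participant meets the inclusion criteria", and a note to the schedule of activities gives it the same purpose. In Section 10, Table 12 describes ITCH4 as "Defined as a ≥ 4-point improvement in CHE-related Itch NRS score from baseline" and names no derivation of baseline.

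SAP 7.4.1.1 has two rules. The first is: "The CHE-related Itch NRS score for baseline will be determined by averaging the 7 daily NRS scores before Day 1". By-visit scores after baseline are 7-day averages too. The second covers all daily itch analyses, including time to itch improvement: "baseline will be defined as the last available Itch NRS score during the last week prior to Day 1".

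SAP 7.4.2 builds the Day 7 endpoint from Day 7 daily scores, multiply imputed where missing, and adds: "The corresponding binary response on Day 7 will be derived for each of the imputed datasets per the definition in Section 7.4.1.1". SAP 7.5.2.2 analyses Day 3 with "models similar to the key secondary endpoint of ITCH4 at Day 7". The title of Figure 4.3.3.2 in SAP Appendix A includes "CHE-Related Daily Itch NRS Score from Day 1 to Day 7 using Multiple Imputation". SAP 6.1.2 lists baseline itch in both forms, by visit and daily. SAP 11.1, on changes to protocol-defined analyses, reads Not applicable.

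**The concern.** Day 7 ITCH4 is the fourth endpoint in the alpha-controlled sequence and shares its name and threshold with the two before it. A protocol reader would expect one baseline for all three. The SAP uses another for Day 7 and does not say so in a single sentence: SAP 7.4.2 points back to a section that holds two baselines.

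The rule decides who counts as a responder. The averaged baseline also ties entry to response, since anyone admitted with an average of at least 4 can in principle fall by 4 points. The last single score breaks that tie. A participant who scores 5 on six days and 3 on the last has an average of 4.71 and is eligible, but cannot fall 4 points from 3. That person can never respond at Day 7 or Day 3, or have a time-to-itch event. At stake are the meaning of the Day 7 rates and their comparability with Weeks 4 and 16.

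**Working it through.** **1. The plan's own figure.** Inputs from Protocol Table 9 and SAP Table 2: 30% vs 10%, 180 participants randomized 1:1 (90 per arm), chi-square test, two-sided alpha 0.05.

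- Pooled rate = (0.30 + 0.10)/2 = 0.20; null SE = sqrt(2 × 0.20 × 0.80/90) = 0.0596.
- SE under the alternative = sqrt((0.30 × 0.70 + 0.10 × 0.90)/90) = 0.0577.
- Power = Φ((0.20 − 1.96 × 0.0596)/0.0577) = Φ(1.44) = 92.5%, against 92% stated.

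The rates are not tied to either baseline, so this figure does not favour one.

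**2. Type I error.** Both baselines come from diary scores for Day −7 to Day −1, before treatment. If treatment has no effect, baseline and Day 7 scores have the same joint distribution in both arms under either rule. Day 7 is last in the sequence, so no later test depends on it.

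**3. The worked example.** Average = (6 × 5 + 3)/7 = 33/7 = 4.71.

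- Single score: 3 − y ≥ 4 has no solution for y ≥ 0.
- Average: 4.71 − y ≥ 4 means y ≤ 0.71, so only a Day 7 score of 0 responds.

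The participant loses one qualifying score. The reverse also occurs: with 5 on six days and 7 on the last, the average is 37/7 = 5.29. The averaged rule then needs y ≤ 1 and the single score y ≤ 3.

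**4. What an averaged baseline would do at Day 7.** The Day 7 score is a whole number. If the average is a whole number plus a fraction f, the smallest fall that qualifies is 4 + f. With seven diary days and remainders 0/7 to 6/7 equally likely, mean f = (0 + 1 + … + 6)/49 = 21/49 = 0.43. The nominal 4-point threshold becomes about 4.4 points on average.

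**5. Size by simulation.** The documents give no diary variability, so every input here is assumed: person mean 6, 6.5 or 7 (SD 1.5); day-to-day SD 1.0, 1.5 or 2.0; lag-1 correlation 0 or 0.5; SD of true change 1.6 or 2.2. That makes 36 scenarios of 200,000 participants. Scores are rounded and held to 0-10, and entry needs an average of at least 4. Mean change is solved to give 30% and 10% under one baseline, and responses are then re-scored under the other.

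| | 30%/10% set under the average, re-scored from the single score | 30%/10% set under the single score, re-scored from the average |
|---|---|---|
| Active rate | 35-39% | 21-24% |
| Vehicle rate | 14-17% | 5-7% |
| Difference (points) | 20-23 | 16-18 |
| Status changes, active | 11-19% | 10-17% |
| Status changes, vehicle | 6-12% | 5-8% |
| Power, 90 per arm | 86-94% | 89-94% |

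Both power ranges straddle 92.5%.

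**6. Participants who cannot respond.** Eligible participants with a last score below 4 make up 1-3%, 3-7% and 6-11% at SDs of 1.0, 1.5 and 2.0. Most would not respond under the average either. In the first calibration, those who would respond under the average but are blocked by a last score below 4 are 0.3-3.0% of active and 0.1-1.0% of vehicle participants. Per arm of 90 that is 0.3-2.7 and 0.1-0.9 people.

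**The case for a change.** The strongest case for a change is textual. Criterion 5 is worded as a definition of baseline itch, not merely as an entry rule, and the protocol offers no other. The SAP leaves the Day 7 choice to inference. Table 5 and the imputation code say only baseline or base, and the title of Table 2.2.6 omits the word daily that its matching figure carries. SAP 4.1.3 adds a general rule that would admit a value from Day 1 itself. Two programmers could, on this argument, derive different responders for an alpha-controlled test. Recording the rule in SAP 11.1 would cost almost nothing.

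Part of this stands: one sentence naming the Day 7 and Day 3 baseline would read better. The inference is nonetheless short. The daily rule covers all daily itch analyses, SAP 7.4.2 calls the Day 7 input a daily score, and the itch-specific rule displaces the general one in SAP 4.1.3. Day 7 could hardly be a by-visit score, because the schedule has no Week 1 visit. Protocol 10.4 leaves detailed analysis to the SAP, so supplying a derivation that Section 10 left open is not clearly a change to a protocol-defined analysis.

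The SAP's multiple imputation at Day 7, where the protocol counts missing as nonresponse, is a separate matter and says nothing about the baseline.

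**Conclusion.** No change follows. The single-score baseline for Day 7 is a fair trade-off that the SAP states, if less directly than it might. It compares one whole-number score with another, so the threshold stays at 4 points, and skin pain follows the same convention (SAP 7.5.1.2). The averaged baseline is less noisy and matches the entry criterion. But it would set a 7-day mean against one whole-number score and still not make Day 7 comparable with Weeks 4 and 16, where the post-baseline value is also a 7-day mean.

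The choice does affect the rates: under the assumed variability, about 10-19% of active and 5-12% of vehicle participants would change status, in both directions. It does not affect the validity of the test, and neither baseline gives more power throughout. This rests on the rule being fixed before unblinding, as Protocol 10.4 (SAP final before database lock) and 10.4.5 (sponsor unblinded after the primary lock) provide. The sizes, unlike the reproduced 92.5%, rest on diary variability that the documents do not give. Noting the rule in SAP 11.1, or adding an averaged-baseline sensitivity analysis, would leave the planned test as it is.

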## 7.4.2. Key Secondary Efficacy Analysis

Key secondary efficacy analyses will be conducted in the ITT population in the DBVC period. If the primary objective is achieved, the statistical comparisons for key secondary endpoints will be tested with the procedures specified in Section 3.2. The same nonresponder imputation method as specified in the primary analysis will be used to handle missing Week 4 and Week 16 itch data.

For the key secondary endpoints of ITCH4 at Week 1 (Day 7), all participants who are missing Day 7 daily Itch NRS scores will be imputed using multiple imputation by fully conditional specification method. The variables to be included in the imputation regression model are treatment group, stratification factor, baseline itch score, and postbaseline daily itch score on Day 1 to Day 7. The corresponding binary response on Day 7 will be derived for each of the imputed datasets per the definition in Section 7.4.1.1.

The following sample SAS code will be used for the MI:

```
proc mi data=mi_wide seed=18424226 nimpute=30 out=impute_itch;
class trt01p strat1 strat2;
var trt01p strat1 strat2 base avald1 avald2 avald3 avald4 avald5
avald6 avald7;
fcs regpmm nbiter=30;
run;
```

All key secondary efficacy analyses will use stratified CMH test similar to the primary efficacy analysis. The summary of key secondary endpoints analysis is also provided in Table 5.

**Table 5:** Summary of Analyses for Key Secondary Endpoints

Parameter	Definition	
Treatment	Ruxolitinib 1.5% cream compared with vehicle cream	
Population	ITT population	
Variables	ITCH4 response at Week 16 ITCH4 response at Week 4 ITCH4 response at Week 1 (Day 7)	
Population-level summary	Stratum-adjusted IGA-CHE-TS rate difference with 95% CI	

Note 1: Participants with missing observed data at the timepoint of interest (Week 4, Week 16), participants who discontinue study treatment at any time before the timepoint of interest (Week 4, Week 16), and participants who discontinue from the study for any reason will be defined as nonresponders. Participants with missing observed data at Day 7 will be imputed using multiple imputation by fully conditional specification method. No rescue therapy or treatment switch is allowed in this study. Note 2: ITCH4 is defined as  $a \ge 4$ -point improvement in CHE-related Itch NRS score from baseline.

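### The Day 7 ITCH4 imputation leaves out the Day 8-14 itch scores the trial already collects; adding them as auxiliary variables would give a small, cheap gain in precision

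*SAP*

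**What the plan says.** SAP 7.4.2 separates Day 7 from the other two ITCH4 endpoints. Weeks 4 and 16 use nonresponder imputation. For Day 7, "all participants who are missing Day 7 daily Itch NRS scores will be imputed using multiple imputation by fully conditional specification method". The model holds treatment group, stratification factors, baseline itch and "postbaseline daily itch score on Day 1 to Day 7". The sample code agrees with the text: its variable list begins "var trt01p strat1 strat2 base avald1 avald2 avald3 avald4 avald5" and ends at `avald7`. It uses predictive mean matching with 30 imputations, after which "The corresponding binary response on Day 7 will be derived for each of the imputed datasets".

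Later scores exist. SAP 7.4.1.1 states: "Participants reported their worst itch severity in the evening beginning on the day of screening through Week 32 or ET". SAP 7.5.2.2 summarises "improvement in CHE-related daily Itch NRS score from baseline to Day 14", and Figure 4.3.3.1 in SAP Appendix A plots daily response to Day 14. SAP section 10 places the primary analysis after every participant has completed the 16-week double-blind period.

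Day 7 ITCH4 is the fourth and last test in the fixed sequence (SAP 3.2).

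**The concern.** Every missing Day 7 score is imputed the same way, whether the participant left the study or skipped one evening. The first clinic visit after baseline is Week 2 (Protocol Table 3), so no scheduled visit falls near Day 7 to prompt a diary entry, and isolated gaps are plausible. For someone who resumes on Day 8, the later scores bear directly on the missing value, yet the model cannot use them. The loss is largest when the gap also covers the days just before Day 7, because the nearest earlier scores are then missing too.

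Using later days fits the plan's own approach. In a fully conditional model, Days 4-7 already inform a missing Day 3 score, and "Statistical analysis for the ITCH4 response at Day 3 will be conducted using models similar" to those for Day 7. Open-label treatment starts only at Week 16 and no rescue or switch is allowed, so Day 8-14 scores from participants still on treatment belong to the randomised comparison. What is at stake is some avoidable imputation variance in an alpha-controlled test, and a somewhat weaker case for missing-at-random when gaps are intermittent.

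**Working it through.** **Inputs from the documents.** 180 participants randomised 1:1, so 90 per arm; Day 7 ITCH4 rates of 30% and 10%; chi-square test, two-sided 0.05; stated power 92% (Protocol 10.1 Table 9, SAP 3.3 Table 2).

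**Assumed, because the documents give no figure.** A fraction f = 10% or 20% of Day 7 scores is missing, all with Days 8-14 observed. The correlation between days i and j is a + (1 - a - e)ρ^|i-j|, where a is the stable between-person share, e is independent daily noise, and baseline is the last score before Day 1.

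**Step 1: the plan's own figure.** Null SE = √(2 × 0.20 × 0.80/90) = 0.0596. Alternative SE = √((0.21 + 0.09)/90) = 0.0577. Power = Φ((0.20 - 1.96 × 0.0596)/0.0577) = Φ(1.44) = 92.5%, which reproduces the stated 92%.

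**Step 2: from one imputed score to the test.** Let r be the residual variance of the Day 7 score given the predictors, on a scale where a daily score has variance 1. Let V = 2(1 - corr(baseline, Day 7)) be the variance of the change. For an arm with response rate π and z = Φ⁻¹(π), the mean conditional p(1-p) is π - Φ₂(z, z; 1 - r/V), where Φ₂ is the bivariate normal distribution function. Let K be the sum of this over arms divided by 0.30 (= 0.21 + 0.09). The variance of the rate difference is then multiplied by 1 + fK.

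*Worked case* (a = 0.6, e = 0.15, ρ = 0.8; only Day 7 missing). The baseline-to-Day 7 correlation is 0.6 + 0.25 × 0.8⁷ = 0.652, so V = 0.695. Adding Days 8-14 takes r from 0.302 to 0.244 and K from 0.654 to 0.587. At f = 20% the multiplier falls from 1.131 to 1.117, a 1.2% reduction.

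| a, e, ρ | Days missing | r without → with Days 8-14 | Variance reduction, f = 10% | f = 20% |
|---|---|---|---|---|
| 0.6, 0.20, 0.5 | 7 | 0.412 → 0.362 | 0.4% | 0.8% |
| | 5-7 | 0.488 → 0.391 | 0.8% | 1.4% |
| 0.6, 0.15, 0.8 | 7 | 0.302 → 0.244 | 0.6% | 1.2% |
| | 5-7 | 0.406 → 0.273 | 1.3% | 2.4% |
| 0.4, 0.10, 0.9 | 7 | 0.248 → 0.183 | 0.8% | 1.5% |
| | 5-7 | 0.387 → 0.214 | 1.8% | 3.3% |
| 0.5, 0, 0.8 (no daily noise) | 7 | 0.188 → 0.110 | 1.1% | 2.1% |
| | 5-7 | 0.418 → 0.160 | 2.6% | 4.9% |

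Dividing 90 per arm by the multiplier in the Step 1 formula turns these into power gains. They run from 0.1 point (first row) to 1.0 point (third covariance, Days 5-7 missing, f = 20%). The noise-free extreme gives 1.5 points.

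**Step 3: simulation.** Predictive mean matching, 30 imputations, Rubin pooling of an unstratified rate difference, 600 runs per scenario, third covariance above. If λ is the share of total variance due to missingness, the reduction is 1 - (1 - λ₁)/(1 - λ₂).

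- 10% missing: λ falls from 0.058 to 0.051, so 1 - 0.942/0.949 = 0.7%.
- 20% missing: 0.110 to 0.097, so 1 - 0.890/0.903 = 1.4%.
- 20% missing with Days 4-6 also unavailable (a four-day gap): 0.149 to 0.107, so 1 - 0.851/0.893 = 4.7%.

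In these scenarios power moved by less than the Monte Carlo error of about 1 point, and the rate difference stayed near 0.20. When missingness was made to depend on the Day 8-14 scores themselves, the mean difference was 0.204 without them and 0.203 with them, against 0.204 for complete data.

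**The case against.** The strongest reply is that this is a preference. The model already contains Day 6 and is valid under missing-at-random given its variables. No stated sample size, alpha or power changes, and Day 7 is the last test in the sequence of a Phase 2 trial. All of that stands, and it is why the point is only an improvement.

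It is also fair that the cut-off matches the planned outputs. Figure 4.3.3.2 limits the multiply imputed display to Days 1-7, and the Day 14 figure is not labelled as imputed. A reader might infer from the Day 14 summary that later scores were meant to be in the model and were left out by mistake. The documents do not support that, since text, code and figure list agree.

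A reader might also infer that the Day 7 result would be biased. Nothing in the documents shows it, and the simulation found no shift.

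A third tempting reading is a large gain, such as the 41% cut in residual variance in the noise-free row (0.188 to 0.110). That figure describes one participant's imputed score, not the test, and assumes a single-item diary score has no independent daily noise. With 15-20% noise the cut for a single missed day is 12-19% (first two covariances).

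Two further objections stand. Days 8-14 have gaps of their own, and some scores may follow a treatment interruption or stop, so the change is not entirely free. And Protocol 10.4.2 (Table 12 note) counts missing Day 7 data as nonresponse, while SAP 11.1 lists no change from the Protocol. If the Protocol rule governs, this point falls away.

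**Conclusion.** The concern holds as a modest efficiency point. The SAP's Day 7 imputation omits later scores that the trial collects and will hold, and nothing in the documents explains why. The planned method remains valid under missing-at-random.

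The gain is roughly 0.4-4% off the variance of the rate difference for gaps of one to three days, or well under to about one point of power. This rests on assumed missingness of 10-20%, later data for everyone missing Day 7, and assumed correlations that include some daily noise. The noise-free extreme reaches 4.9%, but is not a realistic model for a daily 0-10 score. The average gain shrinks in proportion to the share of missing participants who never resume.

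The rule for combining the 30 imputed analyses is also unstated. A reader might infer that the Day 7 test is undefined. That goes too far: SAP 7.3.2 and Table 5 already give a stratified test and a stratum-adjusted rate difference with its interval, and only the combination step is missing.

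**What to change.** In SAP 7.4.2, add `avald8`-`avald14`, or one Day 8-14 summary if a smaller chained model is preferred, to the VAR statement and the model description as auxiliary variables. Use scores recorded while the participant is still on randomised treatment, and add one sentence on how scores recorded after stopping are handled. Use the same imputed datasets for Day 3 ITCH4. In the same edit, state that the Mantel-Haenszel rate difference and its variance are computed in each dataset and combined by Rubin's rules.

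The Protocol 10.4.2 and SAP 7.4.2 rules for missing Day 7 data should be reconciled first. The change should be written down before unblinding.

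The cost is a short code edit, a few SAP sentences and a somewhat larger imputation model. No new data are needed, and sample size and alpha are unchanged.
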